1. Determine any change in pain, fatigue and psychological well-being as a result of SKY in PCa patients.
2. Assess changes in some physiological parameters in response to SKY in the same subjects, compare these with those from Part 1, and assess whether these translate into clinical effects.

Subjects:

PCa patients that have been treated with radiotherapy will be recruited to the study (Winship Cancer Institute Clinic, contact person [name]).

Inclusion criteria: Age \geq 45 years; having finished radiotherapy at least two months ago; ability to speak/read English and give informed consent; having an interest in being part of a study to evaluate yoga-derived exercises and eager to practice some kind of relaxation exercise daily for 3 months.

Exclusion criteria: Having a diagnosis of psychiatric illness or other major illness in addition to PCa, such as other cancers, uncontrolled hypertension, lung disease, liver disease or heart disease.

Approval by the IRB Committee will be applied for. All participants will sign consent forms and throughout the study they will be treated according to the ethical guidelines, in addition to standard treatment for PCa. Participants will be informed that the data obtained in this study will be kept in a separate approved password controlled secure database at the Winship Cancer Institute of Emory University, and that the data from this database will be linked to the approved clinical database in the same institution. They will also be told that they participate by their free will and that they are free to leave the study whenever they wish without giving any reason for it and not risking any consequence for the standard treatment that they will receive.

The men will be randomly assigned to one of two groups:

1. No treatment control.
2. Healing Breath Program (SKY).

SKY includes gentle stretches (yoga postures), specific breathing exercises (see below), and cognitive coping and stressor evaluation strategies. SKY is traditionally understood to dissolve emotional distress and create the subjective experience of rest and well-being. The instructors in SKY are trained by the International Art of Living Foundation. The yoga intervention is held over 13 weeks: in Week 1, subjects will receive yoga instruction for approximately 3 hours daily on 5 consecutive weekdays, and in Weeks 2-13, subjects will attend yoga instruction once a week for about 2 hours.

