The breathing techniques that are part of SKY are: (a) Three-Stage Pranayama with Ujjayi or "Victory Breath", (b) three sets of Bhastrika or "Bellow's Breath", and (c) SK, and they are practiced in that order. The breathing practices are done in a sitting posture, either in a chair or on the floor. Eyes are kept closed throughout the sessions.

A total of 50 patients will be randomized into the two study arms. 20 subjects are aimed at in each group, but to account for drop-out/exclusion, 25 subjects will be recruited per group (to accommodate drop-out/exclusion rate of 20%). Both groups will be tested at the time of recruitment

to the study as Pretest 1. The SKY intervention will be given in groups of 10-15 patients and the tests will be performed again within 2 weeks of the first week of yoga (Posttest 1). The control group will be tested at the same time. Posttest 2 will be performed within 2 weeks of completing the 13-week yoga program, using the same parameters. **In addition to daily home practice, there will be weekly follow-up sessions for the SKY group** which will last about 2 hours during which exercises will be performed in a group and questions that may arise related to the practice will be answered. Control subjects will be offered 1-week of yoga classes after the end of the study (ie, after post-test-2)

Below is a brief flowchart of the study timeline:

Week --	Recruitment (3 months prior to the start of yoga)
Week --	Pretest 1 (within 2 months prior to starting yoga)
Week 1-13	SKY intervention (13 weeks)
Week 2-3	Posttest 1 (within 2 weeks of the first week of yoga)
Week 14-15	Posttest 2 (within 2 weeks of the last week of yoga)

Research design and methods:

Aim 1. Determine any change in pain, fatigue and psychological well-being as a result of SKY in PCa patients.

We will assess psychological wellness parameters in the PCa subjects at the time points as described above. This will be done by administering standardized questionnaires which are enumerated below:

1. The Hospital Anxiety and Depression Scale (HADS): A 14-item self-rating scale, measuring anxiety and depression (Zigmond and Snaith, 1983).
2. The EORTC Quality-of-life Questionnaire (EORTC QLQ-C30). A cancer-specific 30-item questionnaire (Aaronson et al., 1993) incorporating 5-functioning scales, a global health-status/QOL scale and symptoms assessment. In addition Functional Assessment of Cancer Therapy-Prostate (FACT-P) questionnaire will be utilized.

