Week 1 – Yoga instruction (3 hours daily for 5 days)
Week 2-13 –Yoga instruction (2 hours on one day each week)
3. **Post-study evaluations (1):** Questionnaires, and blood/saliva/hair samples (within 2 weeks of the first week of yoga)(Post-test 1) (Week 2-3)
4. **Post-study evaluations (2):** Questionnaires, and blood/saliva/hair samples (within 2 weeks of the last week of yoga)(Post-test 2) (Week 14-15)

Control group:

- 1) Prestudy evaluations: Questionnaires, and blood/saliva/hair samples (after consenting) (Pre-test 1)
- 2) Post-study evaluations (1): Questionnaires, and blood/saliva/hair samples (within 6-8 weeks from the pre-test 1 evaluations)(Post-test 1)
- 3) Post-study evaluations (2): Questionnaires, and blood/saliva/hair samples (within 2-4 months after Post-test 1 evaluations)(Post-test 2)
- 4) Control subjects will be offered 1-week of yoga classes after the end of the study (ie, after post-test-2)

Statistical Considerations:

Fifty subjects should be a sufficient sample size because in our previous study with a sample size of 14 subjects we were able to observe statistically significant changes (Qu et al, 2013). Comparisons will be made with the Student's t test. A value of $P < 0.05$ will indicate statistical significance.

Research team:

The main coordinator of the project is [name], Department of Hematology and Medical Oncology, Emory University. The collaborator partners are: [name], Department of Psychiatry; [name], and [name] from Department of Radiation Oncology, Emory University.

Yoga instructions will be provided by Art of Living Center instructors in Atlanta. They have agreed to provide the SKY intervention proposed in this study.

Epigenetic, biochemical and inflammatory marker laboratory tests will be done at [name] Laboratory. [name] has conducted research using similar methodology (testing of wellness parameters, cancer related endpoints, and gene expression) (Kjellgren et al., 2007; Qu et al., 2013) which will facilitate the current work.

Ethical considerations: All work will be done in accordance with the ethical principles of human subject use and the rules of the Institutional Review Board (IRB) at Emory University. All

members of the research team have participated in similar studies before involving human subjects and are thus familiar with all the procedures that are necessary.

REFERENCES

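### SKY is taught in about two classes, but the planned t test treats all men as independent; if classmates' outcomes are correlated, its standard error is too small

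*Combined protocol and SAP*

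**What the plan says.** Under Subjects, allocation is by individual: "The men will be randomly assigned to one of two groups". One arm is "No treatment control" and the other is SKY. On size, "A total of 50 patients will be randomized into the two study arms", and "20 subjects are aimed at in each group" after an allowance of 20% for drop-out and exclusion.

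Delivery in the SKY arm is collective: "The SKY intervention will be given in groups of 10-15 patients". In week 1, "subjects will receive yoga instruction for approximately 3 hours daily on 5 consecutive weekdays". The weekly sessions that follow are ones "which will last about 2 hours during which exercises will be performed in a group". Home practice runs alongside. Controls are offered yoga classes only after the last assessment.

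Statistical Considerations contains a remark on sample size, the sentence "Comparisons will be made with the Student's t test", and a significance threshold of P < 0.05. It has no class or instructor term, ICC, design effect or number of classes. It also does not say whether the test is paired or two-sample.

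**The concern.** The two arms differ in structure. Control men have no shared sessions, whereas SKY men learn and practise in classes for 13 weeks. Group instruction and discussion could make classmates' outcomes resemble each other, most plausibly on self-reported mood, fatigue and quality of life. Student's t test, paired or two-sample, assumes that men are independent. If classmates do resemble each other, the SKY mean is less precise than the test assumes, and the SE and confidence interval are too narrow. With about two classes, one unusually good or poor class could be read as an effect of SKY as a programme. The plan offers no way to look for this, because it does not say that class membership will be recorded.

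**Working it through.** **Plan's own figure.** 20 / (1 - 0.20) = 25 per arm, so 50 in total. This reproduces exactly. The base of 20 per arm cannot be derived, because no effect size, standard deviation or power is stated.

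**Number of classes.** With 25 SKY men in classes of 10 to 15, the count lies between 25/15 = 1.7 and 25/10 = 2.5. With 20 men it lies between 20/15 = 1.3 and 20/10 = 2.0. Two is the only whole number that fits. The budget's 24 follow-up sessions agree: 2 classes x 12 weeks = 24. The budget also lists four blocks of 16 hours of instruction without explanation. A week-1 course is about 5 x 3 = 15 hours, so these may be four courses, perhaps including those offered to controls. Four SKY classes of about 5 or 6 men would contradict the stated class size, but that case is shown below.

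**Formulas.** Assume a two-sided, two-sample test with equal arms and equal total variance, and clustering in the SKY arm only.
- Design effect in the SKY arm: DE = 1 + (m - 1) x ICC, where m is the mean class size.
- Correct SE divided by t-test SE: sqrt((1 + DE)/2).
- Approximate true error: 2 x [1 - Phi(1.96 / SE ratio)].

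The ICC values are assumptions. The last column is from simulation of the pooled t test (at least 200,000 trials per setting).

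| Setting | ICC | DE | SE ratio | Error, formula | Error, simulated |
|---|---|---|---|---|---|
| 2 classes of 10 vs 20 controls | 0 | 1.00 | 1.000 | 5.0% | 5.0% |
| same | 0.01 | 1.09 | 1.022 | 5.5% | 5.5% |
| same | 0.05 | 1.45 | 1.107 | 7.7% | 7.7% |
| same | 0.10 | 1.90 | 1.204 | 10.4% | about 10.5% |
| Classes of 12 and 13 vs 25 controls (m = 12.5) | 0.01 | 1.115 | 1.028 | 5.7% | 5.7% |
| same | 0.05 | 1.575 | 1.135 | 8.4% | about 8.5% |
| same | 0.10 | 2.15 | 1.255 | 11.8% | 12.0% |
| 4 classes of 5 vs 20 controls | 0.05 | 1.20 | 1.049 | 6.2% | 6.1% |

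Unequal classes of 10 and 15 give nearly the same result as 12 and 13: 8.6% at ICC 0.05 and 12.2% at 0.10. At ICC 0.05 with two classes of 10, the 20 SKY men carry the information of 20/1.45 = 13.8 independent men.

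**Within-SKY change.** Aim 2 speaks of comparing endpoints across time points, which may mean paired tests within the SKY arm. There the whole sample is clustered and the SE ratio is sqrt(DE): sqrt(1.45) = 1.20 at ICC 0.05 and sqrt(1.90) = 1.38 at 0.10 (m = 10).

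**Can a class term repair it?** Not with two classes, which leave one degree of freedom for the class variance. A class-mean test with Satterthwaite degrees of freedom still has 6.5% to 8.2% error over ICC 0 to 0.10. At an assumed effect of 0.909 SD, which 20 per arm detects with 80% power by the ordinary t test, its power is 61% at ICC 0 and 52% at ICC 0.05.

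**The case against.** The strongest objection is that nothing in the documents shows a positive ICC, least of all for antioxidant enzymes, cytokines, hair cortisol or methylation. Men are randomised individually, so if neither SKY nor its classes affect anyone, the t test keeps about 5%. Both points stand. Inflation arises only when class effects exist around a zero mean effect, and at ICC 0.01 it is small. However, the t test itself assumes an ICC of exactly zero without saying so, and a claim about SKY as a programme, beyond these particular classes, has to allow for class effects.

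A reader might infer more than the documents support:
- **That the error rate is above 5% for every questionnaire and biomarker.** This would need a positive ICC for each outcome, and none is given.
- **That classmates share one instructor.** The protocol refers to instructors in the plural and does not allocate them to classes. It also does not say that class membership stays fixed for 13 weeks.
- **That a detectable difference must be restated.** The plan states none.
- **That significance should be judged at a fixed ICC of 0.05.** With two classes of 10, that rule gives about 3.1% error if the true ICC is 0 and about 7.4% if it is 0.10, so it does not guarantee 5% either. It would also make conclusions for very different outcomes depend on one assumed value.

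**Conclusion.** The point holds conditionally. Group delivery in one arm, about two classes, and a test that ignores classes are all established by the documents. If classmates' outcomes are positively correlated, the two-sample t-test SE with two classes of 10 is too small by a factor of 1.11 at ICC 0.05 and 1.20 at 0.10. The corresponding error around a zero mean effect is about 7.7% and 10.5%. With 25 analysed per arm it is about 8.4% and 12%, and with four classes of 5 it would be about 6.1% at ICC 0.05. These figures rest on assumed ICCs, a two-sided two-sample test, equal arms and equal variances. The documents do not support saying that the stated 5% is certainly missed. What they support is that the plan has no means of showing whether a result survives plausible clustering.

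**What to change.** - Record each SKY man's class, and state the number of classes and what the budget's four instruction blocks cover.
- In Statistical Considerations, state which comparisons are two-sample and which are paired.
- Pre-specify that each SKY-control difference is reported with the ordinary t-test result and with SE, confidence interval and P value recalculated at ICC 0.01, 0.05 and 0.10. Multiply the SE by sqrt((1 + DE)/2) for equal-arm two-sample comparisons, with DE = 1 + (m - 1) x ICC and m the mean analysed class size. For any within-SKY change, use sqrt(DE).
- Describe a result that loses significance within that range as not robust to class clustering. Do not make one fixed ICC the sole rule for significance.
- State as a limitation that two classes cannot estimate the class variance.

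**Cost.** Recording class is one data item, and the rest is wording and a little more analysis work. With 20 per arm in two classes of 10, the recalculated SKY-control intervals are about 2%, 11% and 20% wider at ICC 0.01, 0.05 and 0.10. Randomisation, sample size and delivery do not change.

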3. The Life Orientation Test – Revised (LOT-R): A 10-item self-report scale, measuring expectations about positive outcome in general (Scheier et al., 1994)
4. 36-item short-form health survey (SF-36) vitality scale, a reliable and valid measure of energy/fatigue in the past month (Stein et al., 1998).
5. Pain will be assessed with the BPI-SF questionnaire (Cleeland and Ryan, 1994).

Aim 2. Assess changes in some physiological parameters in response to SKY.

In addition to the self-report measures described above, it is important to use objective measures to determine if SKY practice results in physiological effects. As reviewed above, previous studies on SKY have indicated various physiological effects, such as positive influence on the immune system, support of the antioxidants system, and effects of gene expression in the circulating immune cells. To evaluate if similar effects are observed in PCa patients, and whether these correlate with the measures in Part 1, venous blood, saliva, and hair will be collected at the three time points and the following tests will be performed:

1. Enzymes indicative of antioxidant status, i.e. Superoxide Dismutase (SOD) and Glutathione peroxidase (GPX) (based on previous studies by Sharma et al., 2003). We will also measure serum 8-isoprostane level, an indicator of oxidative stress.
2. Inflammatory markers, i.e. Interleukin 1 and 6, Tumor Necrosis Factor alpha (TNF α), and C-reactive protein (since these cytokines are important in carcinogenesis and may be modulated by psychosocial intervention therapies).
3. Saliva cortisol taken between 07 and 09 am, as measure of psychophysiological stress (Levine et al., 2007).

4. Hair cortisol, using a 1-inch strand of hair taken from the back of the head, as a measure of psychophysiological stress.
In addition, two epigenetic tests will be performed:
5. RNA will be isolated from the peripheral blood mononuclear cells (PBMCs) and gene expression changes will be assessed as previously done in response to the SKY regimen (Qu et al., 2013).
6. DNA will be isolated from the PBMCs and potential DNA methylation changes in response to SKY regimen.

The levels of these endpoints (1-3) and gene expression profiles will be compared during the different time points as described above.

STUDY FLOW CHART:

Yoga group:

1. **Prestudy evaluations:** Questionnaires, and blood/saliva/hair samples (within 2 months prior to starting Yoga instructions)(Pre-test 1)
2. **Yoga instructions**

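### The scale for the Aim 2 biomarkers is not stated; read plainly, the plan is an unadjusted raw-scale t test, which would lose power if the markers are right-skewed

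*Combined protocol and SAP*

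**What the plan says.** Under Research design and methods, Aim 2, the protocol plans SOD, GPX and serum 8-isoprostane (item 1), "Inflammatory markers, i.e. Interleukin 1 and 6, Tumor Necrosis Factor alpha" and CRP (item 2), saliva cortisol (item 3) and hair cortisol (item 4), each at three time points. It then says: "The levels of these endpoints (1-3) and gene expression profiles will be compared during the different time points as described above".

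Statistical Considerations gives the method for every endpoint in the trial: "Comparisons will be made with the Student's t test", followed by "A value of $P < 0.05$ will indicate statistical significance".

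The sample size appears under Subjects: "20 subjects are aimed at in each group, but to account for drop-out/exclusion, 25 subjects will be recruited per group". No effect size, SD or power is given. The only justification begins "Fifty subjects should be a sufficient sample size because in our previous study with a sample size of 14 subjects" and refers to significant changes seen in that study.

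The documents name no transformation, distribution check, rank-based alternative, adjustment for Pretest 1 or rule for values below an assay limit. They also do not say whether the t test is paired or between arms. The sentence on comparing levels covers items 1-3, so hair cortisol is reached only by the general t-test sentence.

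**The concern.** Concentrations are positive, and markers of this kind are often right-skewed. With about 20 men per arm, a few high values can dominate a raw mean and, above all, its standard error. If SKY acts roughly proportionally on such a marker, a t test on logged values uses the same data more efficiently.

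The protocol relies on these markers as its objective evidence of a physiological effect. Avoidable loss of power makes it more likely that a real effect is missed and that the result is read as no physiological effect. Leaving the scale open also means it could be chosen after the results are seen.

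**Working it through.** **The plan's own figure.** 20 evaluable per arm with 20% drop-out gives 20 / (1 − 0.20) = 25 per arm, or 50 in total. This reproduces the plan. The 20 itself cannot be derived, because no effect, SD or power is given.

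**Inputs from the documents.** Student's t test, significance at 0.05 (two-sided assumed), 20 evaluable per arm.

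**Assumptions.** The marker is lognormal with natural-log SD σ; SKY multiplies it by a ratio r; the correlation of log values between Pretest 1 and post-test is 0.6 where baseline is used. The documents give none of these, so σ and r are varied.

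**Log-scale power by formula.** The standardised effect is d = |ln r| / σ and the noncentrality is d × √(20/2) = 3.162 d, with 38 degrees of freedom. At σ = 0.8:

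- r = 0.5: d = 0.693/0.8 = 0.866, noncentrality 2.74, power about 76%.
- r = 0.6: d = 0.511/0.8 = 0.639, noncentrality 2.02, power about 51%.
- r = 0.7: d = 0.357/0.8 = 0.446, noncentrality 1.41, power about 28%.

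Baseline adjustment multiplies the residual SD by √(1 − 0.6²) = 0.8, so σ = 0.8 becomes 0.64.

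**Raw-scale power by simulation.** There were 20,000 or more trials per setting, with the same data tested raw and logged, between arms, at one post-test.

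| σ = 0.8, n = 20 per arm | Unadjusted, raw / log | Adjusted for Pretest 1, raw / log |
|---|---|---|
| 50% reduction | 64% / 76% | 77% / 91% |
| 40% reduction | 40% / 51% | 52% / 68% |
| 30% reduction | 22% / 28% | 29% / 39% |

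The scale alone is worth 6 to 12 points without adjustment and 10 to 16 points with it.

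**Dependence on σ (unadjusted, raw / log).**

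| σ | 50% reduction | 30% reduction |
|---|---|---|
| 0.3 | 100% / 100% | 95% / 96% |
| 0.5 | 98% / 99% | 55% / 59% |
| 1.0 | 40% / 57% | 13% / 19% |
| 1.2 | 25% / 43% | 9% / 15% |

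For reference, the coefficient of variation of a lognormal is √(exp(σ²) − 1): about 31% at σ = 0.3, 53% at 0.5 and 95% at 0.8.

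**Within-arm reading.** If the comparison over time points means a paired test within an arm, with the effect set to give 80% power on the log scale, raw power is 77-78% at σ = 0.3 and 61-63% at σ = 0.8 (correlation 0.5 to 0.7). The direction is the same.

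**Type I error.** With no effect and 20 per arm, the raw test rejects 4.1% at σ = 0.8 and 3.4% at σ = 1.2; the log test stays near 5%.

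**Cost when the marker is not skewed.** For normal data with a coefficient of variation of 20%, power is 80% raw and 79% log; at 25% it is 80% and 77%.

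**The case against.** The strongest reply is that the plan never says raw scale. A t test on logged values is still a Student's t test, so the defect is inferred from silence. That stands, and it is why the point is a request to state the scale. A plan that speaks of comparing levels and names no transformation is nevertheless most naturally read as raw.

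It can also be said that neither skewness nor any effect size is in the documents. That stands too: the size of the loss is conditional, and for near-symmetric markers, which may include SOD and GPX, there is little or nothing to gain.

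Four stronger readings are tempting, and the documents do not support them:

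- **A 35-point loss.** For a halving at σ = 0.8, between-arm tests of change from baseline give 50% raw against 85% log. The plan does not name a change-score analysis, and with adjustment on both scales the gap is 14 points (77% against 91%).
- **Outlier-driven false positives.** In these simulations the raw test is conservative, so skewness costs power and does not inflate false claims.
- **A log analysis would rescue Aim 2.** For a 30% reduction at σ = 0.8 it reaches only 28% unadjusted and 39% adjusted. A modest effect would usually be missed on either scale.
- **A threat to the whole trial.** No primary endpoint is named, and the Aim 1 questionnaires are untouched.

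**Conclusion.** The concern holds in a conditional form. The plan does not state the analysis scale for the biomarkers, and its plain reading is an unadjusted raw-scale t test. If the markers are right-skewed and the effect is roughly proportional, that test is less efficient than a log-scale analysis of the same data. At log-SD 0.8 and 20 men per arm, the loss is 6 to 12 points for reductions of 30% to 50% without baseline adjustment, and 10 to 16 points with adjustment on both scales. Without adjustment it is negligible at log-SD 0.3, small at 0.5 and larger above 0.8. These figures rest on the assumed lognormal shape, log-SD, effect sizes and correlation of 0.6. The change is worth making because it is cheap and settles the scale before results are seen. It concerns only the Aim 2 markers.

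**What to change.** Add to Statistical Considerations:

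- IL-1, IL-6, TNF alpha, CRP, 8-isoprostane, saliva cortisol and hair cortisol are compared between arms at each post-test on the natural-log scale, adjusted for the log Pretest 1 value, and reported as SKY/control ratios of geometric means with 95% confidence intervals.
- SOD and GPX are adjusted for Pretest 1, and logged only if the baseline data, examined blind to arm, show skewness.
- The rule for values below the assay limit is stated in advance, with a rank-based sensitivity analysis. The documents give no assay limits, so the rule should be set with the laboratory.

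The cost is a few sentences, with no new samples, visits or participants. The downside is that effects become ratios of geometric means instead of differences in mean concentration, which changes the quantity estimated. A marker that proves near-symmetric gains little or nothing and may lose a few points of power.

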Another study found significantly lower levels of blood lactate in practitioners of SKY compared with the control group. Conversely, the levels of superoxide dismutase (SOD), catalase, and glutathione, three major defenses against oxidative stress, were all found to be significantly higher in SKY practitioners compared with the control group (Sharma et al., 2003). These data suggest that people who practice SKY have an improved antioxidant status and defense against oxidative stress.

Various additional studies indicate that SKY results in improved physical and psychological health. For example, there are interesting findings on the effects of SKY on brain function, indicative of a state of wakeful alertness (Bhatia et al., 2003). In addition, there appears to be strengthening of the immune system, as measured by increases in natural killer (NK) cell number, in both healthy people, but also in cancer patients (Kochupillai et al., 2005). Furthermore, SKY has been shown to be effective in post-traumatic stress disorder (Carter et al., 2013) and in a randomized trial **[name]** and co-workers found that it affected the circulating immune cells at the level of gene expression (Qu et al., 2013).

The goal of this proposal is to systematically study the possible impact of SKY on PCa patients. The studies will include not only psychological assessment through self-report questionnaires on pain, fatigue and psychological well-being, but also objective measures on basic physiological parameters, including the stress hormone cortisol and cytokine IL-6. **Our hypothesis** is that there would be a measurable effect of SKY on psychological distress in PCa patients on the

parameters to be tested, and that this will correlate with favorable changes in physiological parameters that may impact disease progression.

Our preliminary data from two clinical trials we conducted in students (Kjellgren et al, 2007) and healthy volunteers (Qu et al, 2013) support our hypothesis (see above, studies by [name] and co-workers, as referenced in Kjellgren and Qu papers). There was decreased anxiety, depression and stress in one study, and improved physiologic changes in the other. These preliminary results give us confidence that the proposed study will show the hypothesized improvements in the health status and physiological parameters of patients with PCa.

Specific Aims:

This study will have two parts:

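### Aim 2 asks whether earlier SKY gene-expression effects recur, but the only stated rule, Student's t at P < 0.05 without false-discovery control, between-arm contrast or similarity criterion, cannot answer that

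*Combined protocol and SAP*

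**What the plan says.** The introduction reports that in an earlier randomised trial of SKY "it affected the circulating immune cells at the level of gene expression", and counts that trial, done in healthy volunteers, among the team's preliminary data. Research design and methods, Aim 2, lists gene expression among the earlier findings and gives the purpose of the sampling: "To evaluate if similar effects are observed in PCa patients, and whether these correlate with the measures in Part 1".

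Item 5 of Aim 2 covers the RNA work: "gene expression changes will be assessed as previously done in response to the SKY regimen". The sentence that closes the list of tests reads: "The levels of these endpoints (1-3) and gene expression profiles will be compared during the different time points as described above". It speaks of time points and does not name SKY versus control as the contrast for expression.

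Statistical Considerations gives one method, "Comparisons will be made with the Student's t test", and one threshold, "A value of $P < 0.05$ will indicate statistical significance". Neither is limited to particular endpoints. The earlier trial appears in that section only to support the sample size: "in our previous study with a sample size of 14 subjects we were able to observe statistically significant changes". No gene list, direction of change or effect size from it is carried into the plan.

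**The concern.** Asking whether similar effects occur requires something to be similar to, and a rule for deciding. The team has a natural comparator in its own earlier trial, but the plan fixes none of that trial's genes or directions as a target and does not say what result would count as similar or not similar.

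An expression profile consists of many values per man. A t test can be applied to it only transcript by transcript, or to some summary that the plan does not define. Transcript by transcript at P < 0.05, some genes will almost always be called significant, up or down, whether or not SKY acts. Comparing time points within the SKY arm would also leave the randomised control arm unused for this endpoint, so changes due to time alone could not be separated from changes due to SKY.

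At stake is what the expression results can be said to show. Choosing a primary questionnaire, or correcting across the other listed laboratory endpoints, would leave this gap open.

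**Working it through.** **The plan's own figure.** The document aims for 20 men per group and allows 20% for drop-out or exclusion. 20 / (1 − 0.20) = 25 per group, 50 in total, which matches. The 20 itself cannot be derived, because no effect size, standard deviation or power is stated. The steps below use 20 per arm.

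**Assumptions not in the documents.** The number of transcripts (100 to 20,000), two-sided tests, and, for the score, 50 genes each shifting 0.4 SD with mean inter-gene correlation ρ of 0.1 to 0.3.

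**Step 1: false positives with no SKY effect.** Expected number per contrast = 0.05 × m.

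| Transcripts m | Expected at P < 0.05 |
|---|---|
| 100 | 5 |
| 1,000 | 50 |
| 10,000 | 500 |
| 20,000 | 1,000 |

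Three time points allow three pairwise contrasts, which would triple these totals. With only 100 genes, if independent, the chance of at least one false positive is 1 − 0.95^100 = 99.4%. Real genes are correlated. In null simulations of 20,000 transcripts in correlated blocks (200 replicates per setting), the mean count stayed near 1,000. The 95% range was 745 to 1,289 in the mildest setting and 482 to 1,805 in the strongest, and no replicate gave zero.

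**Step 2: make-up of the list if SKY does act.** Suppose 200 of 20,000 transcripts truly shift. False positives: 0.05 × 19,800 = 990. Power for one gene at P < 0.05 with 20 per arm is 23% at 0.4 SD and 46% at 0.6 SD, giving about 47 and 91 true positives. The false share of the list is 990 / (990 + 47) = 95% and 990 / (990 + 91) = 92%.

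**Step 3: what one fixed target could do.** For a single score and one between-arm contrast, 20 per arm gives 80% power for a difference of 0.91 SD. With Bonferroni correction over 20,000 transcripts, the detectable difference rises to 2.05 SD.

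For a signed mean of 50 genes, the standardised effect is d × √(m / (1 + (m − 1)ρ)), here with m = 50 and d = 0.4. If only half the genes carry over to these patients, the average shift is 0.2 SD and the effect halves.

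| ρ | √(50 / (1 + 49ρ)) | Effect, full carry-over | Power | Effect, half carry-over | Power |
|---|---|---|---|---|---|
| 0.1 | 2.91 | 1.16 | 95% | 0.58 | 43% |
| 0.2 | 2.15 | 0.86 | 76% | 0.43 | 26% |
| 0.3 | 1.78 | 0.71 | 59% | 0.36 | 20% |

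The 95% confidence interval half-width before baseline adjustment is t(0.975, 38) × √(2/20) = 2.024 × 0.316 = 0.64 SD, wider than every half-carry-over effect in the table.

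**The case against.** The strongest reply is that no sentence assigns the t test to expression profiles. The line in Statistical Considerations is generic, while item 5 points back to the team's earlier work and may bring in that trial's selection and multiplicity steps. This stands in part: the fair charge is that the analysis is not stated here, and a claim that the sponsor has chosen a wrong method is not supported. But nothing in the document says that the back-reference overrides the general rule, so a reader cannot tell which governs.

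A second reply is that the work is exploratory. The budget labels the epigenetic studies as pilot and gives them $4,500, and the statement about similar effects introduces all the Aim 2 assays. This also stands, and is why labelling the analysis exploratory is part of the fix. The question that Aim 2 asks still needs a rule for answering it.

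A reader might infer that this part of the trial can neither confirm nor refute the earlier effect, or that any set of changed genes would be claimed as support. The documents do not support either. The randomised control arm and three sampling times would allow a test fixed in advance; only the pre-specification is missing. How the investigators would read a gene list is not stated anywhere.

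A third reply is that a signed score is one option among several, including a gene-set test or an overlap test, and that it may be weak. That is correct. Nothing in the documents supports 50 genes, 0.4 SD or the correlations used, and the earlier sample was 14 healthy volunteers. The score is therefore offered as a secondary analysis.

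**Conclusion.** The concern holds in a limited form. As written, the expression part of Aim 2 cannot formally answer whether similar effects occur. False-discovery control, a between-arm contrast and a criterion for similarity are all absent, and the only visible rule would flag about 5% of transcripts per contrast by chance. The figure of about 1,000 rests on an assumed 20,000 transcripts; the 5% rate does not depend on that number.

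The gap is in specification, and the planned samples could support a better analysis. False-discovery control and the baseline-adjusted between-arm contrast are the changes that matter most. The signed score helps, but it does not turn this into a decisive replication test. Under full carry-over its power runs from 95% down to 59%; under half carry-over, from 43% down to 20%. It would be tempting to read a null score as showing that the earlier effect was not replicated. With an unadjusted half-width of about 0.64 SD and a different population, a null would not refute the earlier effect and must be read from its confidence interval.

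**What to change.** **Statistical Considerations:** state that the P < 0.05 rule does not govern individual transcripts.

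**Aim 2, item 5 and the comparison sentence:** state that expression is compared between SKY and control at Post-test 2, adjusted for Pretest 1; that transcripts are tested with a variance-moderated t test and reported at a stated false discovery rate; and that this analysis is exploratory. If the reference to earlier practice is meant to bring in an analysis method, write that method out.

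**Pre-specified secondary analysis:** before expression data are seen by arm, fix the list and directions of the genes that changed in the earlier trial. For each man, compute one score as the mean of standardised log expression, signed by the earlier direction. Report the SKY-versus-control difference in this score at Post-test 2, adjusted for the Pretest 1 score, with its 95% confidence interval.

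**Cost:** protocol wording and a little extra analysis of data already planned, with no new samples, visits or patients. The gene list will be shorter than a P < 0.05 list, and the score depends on carry-over from a small healthy-volunteer study to men treated for prostate cancer.
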